The first dose of the study drug should be administered at Visit 1 after the visit procedures are completed. Further administration of the study product will be made according to the dosing scheme. The subject will administer the study drug and will be followed for 12 weeks during which additional three visits will be made. At Visit 2 (Week 4), Visit 3 (Week 8) and Visit 4 (Week 12) the physician will record patients' complaints and physical examination data, fill HAM-A scale, check the study and concomitant therapy, assess treatment safety and patient compliance with the study treatment. At the final Visit 4 the subject will fill EQ-5D-3L questionnaire and the investigator will determine Clinical Global Impression Scale Efficacy Index (CGI-EI) score.

The patients will be allowed to take symptomatic therapy and medications for their comorbidities during the study, except for the medicines listed in "Forbidden concomitant therapy".

Inclusion and exclusion criteria

Inclusion criteria

- 1. Age between 18 and 45 years old inclusively.
- 2. Diagnosis of somatoform, stress-related and other neurotic disorders (F43, F45, F48)¹ established according to ICD-10 study diagnostic criteria.
- 3. Clinically relevant anxiety at screening (≥ 11 points according to HADS scale).

¹ Diagnosis of diseases and diagnostic procedures to verify somatoform, stress-related and other neurotic disorders in the subjects will not be the study objective; the diagnostics algorithm will be defined by the investigator.

- 4. Availability of signed patient information sheet (Informed Consent form) for participation in the clinical trial.
- 5. Usage of contraceptive methods² by both gender patients of reproductive age during the trial and within 30 days of ending the participation in the trial.

Exclusion criteria

- 1. Expressed depression symptoms at screening (≥ 11 points according to HADS scale).
- 2. Organic including symptomatic, mental disorders (F00-09).
- 3. Mental disorders or behavioural disorders associated with psychoactive substances (F10-19).
- 4. Schizophrenia, schizotic conditions and delusional disorders (F20-29).
- 5. Mood disorders [affective disorders] (F30-39).
- 6. Phobic (F40) and other anxiety disorders (F41), obsessive-compulsive disorder (F42), dissociative [conversion] disorders (F44), depersonalization syndrome (F48.1).
- Behavioural syndromes associated with physiological disorders and physical factors (F50-59).

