- 8. Personality and behavioural disorders at mature age (F60-69).
- 9. Mental deficiency (F70-79).
- 10. Inflammatory and traumatic injuries of brain with persistent neurological deficit.
- 11. Prior diagnosis of heart failure defined by the New York Heart Association classification (1964) as III or IV FC.
- 12. Malignant neoplasm/suspected malignant neoplasm
- 13. Patients allergic to/intolerant of any constituent of the medications used in the treatment.
- 14. Malabsorption syndrome, including congenital or acquired lactase deficiency (or any other disaccharidase deficiency) and galactosemia.
- 15. Any conditions which, according to the investigator, may interfere with the subject's participation in the study.
- 16. Scheduled hospiralizations, surgeries during the study.
- 17. Patients who, from the investigator's point of view, will not comply with the observation requirements of the study or adhere to study drug dosing regimens.
- 18. Use of any medicine listed in the section "Prohibited concomitant treatment" within 30 days preceding the inclusion in this study.
- 19. Drug addiction, alcohol usage in the amount exceeding 2 units of alcohol per day³.
- 20. Pregnancy, breast-feeding.

² Acceptable contraception includes intrauterine device; barrier method (condom, contraceptive cap, cervical cap or spermicide), previous surgical sterilization or vasectomy (for male subjects or partners). Throughout the study systemic hormonal contraceptives including oral contraceptives will not be allowed.

³1 unit of alcohol is equivalent to 0.33 L of lager/150 mL of unfortified wine, or 40 mL of a spirit

- 21. Participation in other clinical trials in the previous 3 months.
- 22. Patients who are related to any of the on-site research personnel directly involved in the conduct of the trial or are an immediate relative of the study investigator. 'Immediate relative' means husband, wife, parent, son, daughter, brother, or sister (regardless of whether they are natural or adopted).
- 23. Patients who work for OOO "NPF "Materia Medica Holding" (i.e. the company's employees, temporary contract workers, appointed officials responsible for carrying out the research or immediate relatives of the aforementioned).

Criteria for Withdrawal or Termination

- 1. Participant's failure or decline to comply with the protocol requirements.
- 2. Necessity for prescribing medications not permitted during the study.

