- 3. An adverse event requiring discontinuation of the study product;
- 4. Pregnancy.
- 5. Patient's decision to withdraw early for lack of efficacy or other reasons.
- 6. Eligibility error.
- 7. Cases not stipulated in the protocol where the investigator decides that further participation may harm the patient.

Number of subjects

It is planned to include 390 subjects, which is expected to yield at least 310 patients completing all protocol procedures.

Interim analysis

An interim statistical analysis is not scheduled within the study.

Treatment

Group 1

Name of the medicinal product: Tenoten

Active ingredient: Affinity purified antibodies to brain-specific S-100 protein - 0.003 g*

* applied onto lactose as a water-alcohol mixture containing no more than 10^{-15} ng/g active form of the API.

Excipients: Lactose monohydrate (lactose) - 0.267g (Eur. Ph.⁴, USP⁵ NF, BP⁶)

Microcrystalline cellulose - 0.03 g (Eur. Ph., USP NF, BP)

Magnesium stearate - 0.003 g (Eur. Ph., USP NF, BP)

⁴ Eur. Ph. European Pharmacopoeia (current edition)

⁵ USP – current US Pharmacopeia

⁶ EP – current European Pharmacopoeia

Method of administration: Tablet for oral use. Dose per administration: 2 tablets. 2 tablets twice daily (4 tablets/day). The tablets should be held in the mouth until dissolution, without meal.

Dosage form: Tablets.

Description: White to off-white, round, flat, scored on one side and beveled tablets.

Storage conditions: Store in a place protected from light at a temperature below 25 C. Keep out of the reach of children.

Group 2

Name of the medicinal product: Placebo

Active ingredient: NA

Excipients: Lactose monohydrate (lactose) - 0.267 g (Eur. Ph⁴., USP⁵ NF, BP⁶)

Microcrystalline cellulose - 0.03 g (Eur. Ph., USP NF, BP)

Magnesium stearate - 0.003 g (Eur. Ph., USP NF, BP)

Method of administration: Tablet for oral use. Dose per administration: 2 tablets. 2 tablets twice daily (4 tablets/day). The tablets should be held in the mouth until dissolution, without meal.

Dosage form: Tablets.

Description: White to off-white, round, flat, scored on one side and beveled tablets.

Storage conditions: Store in a place protected from light at a temperature below 25 C. Keep out of the reach of children.

Group 3

Active ingredient: Affinity purified antibodies to brain-specific S-100 protein - 0.003 g* * *applied onto lactose as a water-alcohol mixture containing no more than* 10^{-15} ng/g active form of the API.

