Excipients: Lactose monohydrate (lactose) - 0.267g (Eur. Ph.⁷, USP⁸ NF, BP⁹)

Microcrystalline cellulose - 0.03 g (Eur. Ph., USP NF, BP)

Magnesium stearate - 0.003 g (Eur. Ph., USP NF, BP)

Method of administration: Tablet for oral use. Dose per administration: 2 tablets. 2 tablets 4 times daily (8 tablets/days). The tablets should be held in the mouth until dissolution, without meal.

Dosage form: Tablets.

Description: White to off-white, round, flat, scored on one side and beveled tablets.

⁷ Eur. Ph. European Pharmacopoeia (current edition)

⁸ USP – current US Pharmacopeia

⁹ EP – current European Pharmacopoeia

Protocol No. MMH-TN-001 19-Apr-2016 Storage conditions: Store in a place protected from light at a temperature below 25 C. Keep out of the reach of children.

Group 4

Name of the medicinal product: Placebo

Active ingredient: NA

Excipients: Lactose monohydrate (lactose) - 0.267 g (Eur. Ph⁴., USP⁵ NF, BP⁶)

Microcrystalline cellulose - 0.03 g (Eur. Ph., USP NF, BP)

Magnesium stearate - 0.003 g (Eur. Ph., USP NF, BP)

Method of administration: Tablet for oral use. Dose per administration: 2 tablets. 2 tablets 4 times daily (8 tablets/days). The tablets should be held in the mouth until dissolution, without meal.

Dosage form: Tablets.

Description: White to off-white, round, flat, scored on one side and beveled tablets.

Storage conditions: Store in a place protected from light at a temperature below 25 C. Keep out of the reach of children.

Treatment duration

Tenoten/Placebo treatment duration is 12 weeks.

Observation period

In total the patients will be monitored for 12 weeks.

Symptomatic (Standard) treatment

Subjects are allowed to receive medications used to treat coexisting diseases other than those representing exclusion criteria, except drugs listed in section "Forbidden concomitant therapy".

Prohibited concomitant therapy

Within 4 weeks prior to enrollment and during the study (beginning from signing informed consent form and initiation of screening) subjects are not allowed to receive any medications that may affect mental and emotional status (parenthesized is the ATC group):

- 1. Psycholeptics (ATC group N05), including antipsychotics, anxiolytics (tranquilizers), hypnotics and sedatives.
- 2. Psychoanaleptics (ATC group N06) including antidepressants, psychostimulants, nootropic drugs and their combinations.
- 3. Antiepileptic drugs (ATC group N03A).
- 4. Anticholinergic drugs (ATC group N04A).

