Procedure/visit	Visit 1 (Day 1)	Visit 2 (Week 4±3 days)	Visit 3 (Week 8±3 days)	Visit 4 (Week 12±3 days)
Informed consent	+			
Collection of complaints	+	+	+	+
Medical history	+			
Physical examination	+	+	+	+
HADS scale filling	+			
HAM-A scale filling	+	+	+	+
EQ-5D-3L questionnaire filling	+			+
Pregnancy test	+			
Concomitant therapy	+	+	+	+
Inclusion/exclusion criteria	+			
Randomization and prescription of study therapy	+			
Study drug supply	+	+	+	
Study drug accountability, compliance assessment		+	+	+
CGI scale filling				+
Evaluation of treatment safety		+	+	+

Schedule of study procedures

Statistical Analyses

Samples

Total set includes all the subjects who have signed ICF. This sample will consider all adverse events throughout the study, including those occurred prior to the study therapy.

The sample including all subjects who received at least one dose of the study product to be used for *analysis of the study treatment safety and tolerability* (*Safety population*), as all adverse events identified after the study product administration will be recorded.

Full Analysis Set This sample will consist of all enrolled subjects, except for those who met at least one of the following criteria:

- 1) failure to meet inclusion/non-inclusion criteria;
- 2) subject failing to take any dose of the study drug;
- 3) absence of any data on the subject after the study drug administration.

This was the best set for the Intention-to-treat method, so it will be used in the *Intention-to-treat efficacy analysis of the test therapy*.

Per Protocol set. This sample includes all subjects who completed the therapy as per the study protocol, without any missing visits or major protocol deviations. This set will be used in the *Per*

Protocol efficacy analysis of the test therapy.

Mean value of the total set for the relevant day will be used to fill lacking/missing data.

Data treatment and all statistical calculations under the protocol will be made using SAS-9.4 statistical software.¹⁰

Evaluation of sample size

The sample size was assessed in accordance with the following rules and assumptions:

- 1. Statistical assumptions
 - 1.1 the power of statistical tests 'P = (1β) ' is 80% (the probability of correct rejection of the null hypothesis is 0.8)
 - 1.2 the probability of type 1 error 'a' is less that 5% (the probability of false acceptance of the alternative hypothesis is less than 0.05);

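### The set used for the intention-to-treat analysis drops subjects for failing any entry criterion, with no limit to facts fixed before randomisation, so no efficacy analysis keeps all randomised, treated subjects

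*Combined protocol and SAP*

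**What the plan says.** All references are to the combined protocol and SAP.

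- **Full Analysis Set** (Statistical Analyses, Samples): "This sample will consist of all enrolled subjects, except for those who met at least one of the following criteria". The three grounds are (1) "failure to meet inclusion/non-inclusion criteria", (2) no dose taken, and (3) "absence of any data on the subject after the study drug administration". The plan then says of this set: "This was the best set for the Intention-to-treat method", and assigns it to the intention-to-treat efficacy analysis.
- **Per Protocol set** (same section): subjects who completed therapy with no missed visit and no major deviation.
- **Inclusion criterion 5**: contraception used "by both gender patients of reproductive age during the trial and within 30 days of ending the participation in the trial".
- **Exclusion criterion 17**: subjects who, in the investigator's view, "will not comply with the observation requirements of the study or adhere to study drug dosing regimens". Exclusion 15 is likewise an investigator's judgement.
- **Criteria for Withdrawal or Termination**: non-compliance with the protocol is item 1. "Eligibility error" is a separate item, number 6.
- **Schedule of study procedures**: consent, the eligibility check and randomisation all fall at Visit 1, and the eligibility check is marked at no later visit.
- **Washout**: exclusion 18 uses 30 days before inclusion. The Prohibited concomitant therapy section says "Within 4 weeks prior to enrollment and during the study".

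**The concern.** An intention-to-treat analysis protects the comparison because membership is settled by randomisation. Removing ineligible subjects afterwards can be defended when ineligibility is an objective fact that predates randomisation, is looked for equally in every arm, and is decided without knowledge of treatment or outcome. Ground (1) carries none of these limits.

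Subjects found ineligible after randomisation are foreseen, since eligibility error is a listed reason for withdrawal. One criterion, inclusion 5, concerns conduct during and after treatment. Its last 30 days fall after the week-12 outcome, so on a literal reading Full Analysis Set membership cannot be settled when the primary endpoint is measured.

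If removals differ between arms and are related to outcome, all three planned comparisons (each Tenoten scheme against pooled placebo, and one scheme against the other) could be biased. No broader efficacy set exists against which to check them.

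**Working it through.** **1. The plan's own figures.** None of them tests an analysis-set definition, but they supply the scale.
- Completers: 2×103 + 2×52 = 310. Inflated for 20% withdrawal: 310/0.8 = 387.5, so 388 against the stated 390. Reproduced.
- Superiority size, with α = 0.05/3 two-sided, 80% power, variance 44 and a difference of 4: 2×(2.394 + 0.842)²×44/4² = 57.6, so 58 as stated. Reproduced.

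Deleting ground (1) does not alter the planned sample size.

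**2. Which subjects each efficacy set keeps.**

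| Randomised subject | Full Analysis Set | Per Protocol set |
|---|---|---|
| Eligible, dosed, some later data, withdrew early | kept | dropped |
| Eligible, dosed, all visits, major deviation | kept | dropped |
| Dosed, with later data, found ineligible | dropped | not kept by any stated rule once withdrawn for eligibility error |
| Dosed, with later data, breached inclusion 5 during the trial | dropped on a literal reading | dropped if counted as a major deviation |

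The third row is the gap: a randomised, treated subject with outcome data whom neither efficacy analysis is sure to include.

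**3. Size, for illustration only.** Let a share f of one arm be removed, and let their mean HAM-A reduction be d points smaller than that of the subjects retained. The full-arm mean is then the retained mean minus f×d, so removal shifts the arm mean by f×d. The documents give neither f nor d. I assume f = 2% to 10% and d = 4 to 10 points.

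*Superiority.* With about 104 per compared group, SE = √44 × √(2/104) = 0.920. With critical value 2.394, the actual two-sided type I error is 1 − Φ(2.394 − f·d/0.920) + Φ(−2.394 − f·d/0.920).

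*Equivalence of schemes.* With 103 per group, SE = √44 × √(2/103) = 0.924. Suppose the true difference sits exactly at the margin, the shift runs towards zero, and the margin is wide enough for the opposite one-sided test to be passed almost always. The error is then about 1 − Φ(2.128 − f·d/0.924), at nominal one-sided 0.05/3.

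| f | d | Shift | Superiority error (nominal 0.017) | Equivalence error (nominal 0.017) |
|---|---|---|---|---|
| 2% | 4 | 0.08 | 0.017 | 0.021 |
| 5% | 6 | 0.30 | 0.023 | 0.036 |
| 10% | 10 | 1.0 | 0.096 | 0.148 |

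These figures put all removals in one arm. With balanced removals unrelated to outcome the shift is zero.

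**4. Offset through pooled placebo.** Placebo is pooled over both schemes (Evaluation of sample size, 1.6). If removals are driven by regimen, the placebo arm on the same scheme loses the same share, and it makes up 52 of 104 pooled subjects. The superiority shift is then about f·d − (f/2)·d = f·d/2, or 0.04 to 0.50 points. At 0.50 the error is 0.034. The comparison of Groups 1 and 3 has no such offset.

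**The case against.** The best defence is that the rule is meant for entry errors only. Eligibility is checked at Visit 1 alone. Later non-compliance has its own withdrawal item, separate from eligibility error. No contraception check is scheduled after the trial, and nothing links a contraceptive lapse to HAM-A. Placebo matches active treatment within each scheme. Much of this stands, and it rules out several stronger readings.

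- *Subjects later judged non-compliant leave through exclusions 15 and 17.* A reader might infer this, but those are entry judgements and nothing turns later non-compliance into an eligibility failure. Inclusion 5 is the only criterion that plainly concerns conduct after randomisation.
- *The main efficacy comparison is biased.* No primary analysis set is named, intention-to-treat and Per Protocol analyses are both listed, and the sample size is built on the Per Protocol number.
- *Both efficacy sets are in effect per-protocol sets.* The Full Analysis Set keeps eligible early withdrawals who have any post-dose data, and withdrawal is planned at 20%.
- *The washout discrepancy changes who is in the set.* Membership follows exclusion 18. The gap of 28 against 30 days is a wording matter.
- *The bias can be expressed as a share of a 3-point margin.* The margin is 0.15×M and M is not given. The 3 points in the plan are the expected upper limit of the difference between schemes.

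The defence does not supply the missing limits: ground (1) is neither confined to pre-randomisation facts nor tied to blinded review. Nor does blinding cover the scheme. Groups 1 and 3 take 4 and 8 tablets a day and no double-dummy is described, so subjects and staff can tell them apart. How far their burden differs is itself unclear: the arm descriptions give the higher scheme as 2 tablets four times a day and the statistical section as 4 tablets twice a day. Those passages must be reconciled.

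**Conclusion.** The point holds as a defect in the definition of the analysis set. Followed as written, the plan drops randomised, treated subjects from the set it labels intention-to-treat, on grounds that need not predate randomisation or be decided blind, and the only other efficacy set is stricter.

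The size of any bias is unknown. The 0.08 to 1.0 points (about half that for superiority if removals follow the regimen) rest wholly on assumed values of f and d and on removals confined to one arm. The documents do not show that removals will be unequal or related to outcome. They only fail to guard against it. Grounds (2) and (3) are not at issue here.

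**What to change.** 1. Delete ground (1) from the Full Analysis Set. Define the set as all randomised subjects who took at least one dose and have any post-dose data, analysed as randomised. Leave ineligible subjects out of the Per Protocol set only.
2. If an eligibility exclusion is kept, limit it to objective criteria fixed before randomisation (so not inclusion 5), decided at blinded review and applied alike in all arms. Add a sensitivity analysis that includes those subjects.
3. As a separate tidy-up, reconcile the 30-day and 4-week washout wordings.

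**Cost.** This is SAP wording, with no change to sample size. A few ineligible subjects enter the analysis and may slightly dilute the effect. Because eligibility errors lead to withdrawal, some of these subjects will lack a week-12 score. The plan fills missing values with the mean of the total set for that day, which pulls the arms together and so favours the equivalence claim. The Per Protocol result should therefore be shown beside the Full Analysis Set result, for equivalence above all.

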 - 1.3 statistical criteria of intergroup comparisons will be two-sided, equivalence criterion one-sided;
 - 1.4 calculation of sample size will be based on the assumptions on the expected effect declared in the primary efficacy criterion of the protocol;
 - 1.5 ratio between sample sizes of Tenoten and Placebo groups receiving similar dosing schemes will be 2:1 (1 Placebo patient 2 Tenoten patients);
 - 1.6 statistical analysis will utilize pooled Placebo group including Placebo with dosing scheme 2 tablets 2 times and Placebo group with dosing scheme 4 tablets 2 times a day, as the differences between Placebo groups with different dosing schemes are not suggested;
 - 1.7 the study is supposed to use three groups of statistical hypotheses; for this purpose probability of type I error α will be corrected by introducing the relevant correction for three hypotheses (α =0.05/3);
 - 1.8 statistical hypotheses will be as follows:
 - 1.8.1. null and alternative hypotheses on superiority of the study product with dosing scheme 2 tablets 2 times a day:

H₀: $\Delta \mu_{T1} = \Delta \mu_{\Pi}$

$H_a: \Delta \mu_{T1} \neq \Delta \mu_{\Pi},$

where $\Delta \mu_{\tau 1}$ – mean reduction (initial – final score) of HAM-A total score in Tenoten group with dosing scheme 2 tablets 2 times a day, $\Delta \mu_{\Pi}$ – mean reduction (initial – final score) of HAM-A total score in Placebo group;

1.8.2. null and alternative hypotheses on superiority of the study product with dosing scheme 4 tablets 2 times a day:

H₀: $\Delta \mu_{T2} = \Delta \mu_{\Pi}$

¹⁰ Holder of license: OOO "NPF "Materia Medica Holding", No. 70100045.

H_a: $\Delta \mu_{T2} \neq \Delta \mu_{\Pi}$,

where $\Delta \mu_{r2}$ – mean reduction (initial – final score) of HAM-A total score in Tenoten group with dosing scheme 4 tablets 2 times a day, $\Delta \mu_{\pi}$ – mean reduction (initial – final score) of HAM-A total score in Placebo group;

1.8.3. null and alternative hypotheses on equivalence of the study product with dosing scheme 2 tablets 2 times a day with the study product with dosing scheme 4 tablets 2 times a day:

$$\begin{split} H_0: & |\Delta \mu_{T1} - \Delta \mu_{T2}| \geq \delta \\ H_a: & |\Delta \mu_{T1} - \Delta \mu_{T2}| < \delta, \end{split}$$

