where μ_{T1} – mean reduction (initial – final score) of HAM-A total score in Tenoten group with dosing scheme 2 tablets 2 times a day, μ_{T2} – mean reduction (initial – final score) of HAM-A total score in Tenoten group with dosing scheme 4 tablets 2 times a day, δ – equivalence margin accepted as 0.15*M where M – mean total population score at baseline;

- 1.9 calculation of sample size for statistical criteria will be made using the group of formulas:
 - 1.9.1. calculation of sample size to evaluate superiority of the study product over placebo:

$$n_1=n_2=\frac{2(z_{\alpha/2}+z_\beta)^2\sigma^2}{\epsilon^2}$$

where $\mathbf{n_1}$, $\mathbf{n_2}$ is sample size for the study product group; ε – expected difference in mean reduction of the total score between Placebo and Tenoten groups; $\boldsymbol{\sigma}$ – standard deviation of mean reduction of the total score (calculated as standard deviation of difference between two uncorrelated random variables); $z_{\alpha/2}$ – tabular value of two-sided z-test for α value; z_{β} – tabular value of one-sided ztest for β value;

1.9.2. calculation of sample size for equivalence evaluation:

$$n_1 = n_2 = \frac{2(z_{\alpha} + z_{\beta/2})^2 \sigma^2}{(\delta - |\epsilon|)^2},$$

where $\mathbf{n_1}$, $\mathbf{n_2}$ is sample size for the study product group; ε – expected difference in mean reduction of the total score between Tenoten with dosing scheme 2 tablets 2 times a day and Tenoten with dosing scheme 4 tablets 2 times a day; $\boldsymbol{\sigma}$ – standard deviation of mean reduction of the total score (calculated as standard deviation of the difference between two uncorrelated random variables); z_{α} – tabular value of z-test for α value; z_{β} – tabular value of z-test for β value, δ – equivalence margin accepted as 0.15*M where M – mean total population score at baseline;

1.10 sample size will be determined using the formula:

N_{PP}=max{ n_i, all pairs of interest (i)},

where N_{PP} – Per Protocol sample size; n_i – result of calculation in cl. 1.6, i.e. the result for each of the three study hypotheses;

1.11 final sample size will be determined using the formula:

$$N_T = N_{PP} / (1 - C_w),$$

where N_T – final sample size; N_{PP} – result of calculation in cl. 1.7, i.e. the scheduled number of the subjects completing the study per protocol; C_w – withdrawal coefficient.

2. Assumptions on expected clinical study effects:

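### The Per Protocol set keeps completers only; if poor responders withdraw, the two Tenoten schemes look more alike in it and equivalence can be declared too easily

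*Combined protocol and SAP*

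**What the plan says.** Under Statistical Analyses, Samples, the Per Protocol set is described as follows: "This sample includes all subjects who completed the therapy as per the study protocol, without any missing visits or major protocol deviations". Entry depends on finishing and attending every visit as well as on adherence.

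The list under Criteria for Withdrawal or Termination includes reasons that can reflect how treatment went: "Necessity for prescribing medications not permitted during the study" (item 2), an adverse event that requires stopping the study product (item 3), and "Patient's decision to withdraw early for lack of efficacy or other reasons" (item 5). The Schedule of study procedures has HAM-A at Day 1 and Weeks 4, 8 and 12, so a subject who leaves late may already have one or two post-baseline scores.

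Under Evaluation of sample size, item 1.8.3 sets the equivalence hypothesis for the two Tenoten schemes. The margin is given as "equivalence margin accepted as 0.15*M where M – mean total population score at baseline", but M is not stated. Items 1.10 and 1.11 size the trial on the Per Protocol number, "the scheduled number of the subjects completing the study per protocol".

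The Samples section also has a Full Analysis Set for the intention-to-treat efficacy analysis, and fills missing values with the mean of the total set for that day. It does not say which set decides equivalence, or whether both must agree.

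**The concern.** Leaving because the treatment is not working is an outcome, not a protocol deviation. A set that requires completion therefore selects on response. If subjects in both schemes leave at about the same level of poor response, the scheme with the lower mean has more subjects below that level and loses more of them. The completers' means then move together.

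In a superiority test that shrinkage costs power. In an equivalence test it favours the claim. Equivalence drives the sample size here (103 per Tenoten group, against 58 for superiority), and it bears directly on the second study objective, the comparison of the two schemes.

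**Working it through.** **Inputs from the plan.** Variance of the HAM-A change 44; schemes expected to differ by less than 3; alpha 0.05/3 = 0.0167 (item 1.7), one-sided for equivalence (item 1.3); 103 per Tenoten group; 20% withdrawal.

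**Assumed, not in the plan.** M = 20, so the margin is 0.15 × 20 = 3; the share leaving for poor response; the correlation between visits; mean reductions at Weeks 4, 8 and 12 of 50%, 80% and 100% of the Week 12 value.

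**1. The plan's figure.** With a working margin of 3, n = 2(z + z)² × 44 / 3².
- One-sided 0.025 with z for β/2: 2 × (1.960 + 1.282)² × 44 / 9 = 102.7, so 103.
- Two-sided 0.05/3 with z for β: 2 × (2.394 + 0.842)² × 44 / 9 = 102.4, so 103.
- The printed formula 1.9.2 with one-sided 0.05/3: 2 × (2.128 + 1.282)² × 44 / 9 = 113.7, so 114.

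The stated 103 is reproduced by a standard variant with a margin of 3, though not by the printed formula at the corrected alpha. Superiority gives 2 × (2.394 + 0.842)² × 44 / 16 = 57.6, so 58, as stated.

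**2. Hand formula.** With 103 completers per scheme, SE = √(2 × 44 / 103) = 0.924. Equivalence is declared if the observed difference is below 3 − 2.128 × 0.924 = 1.03 (the lower bound hardly matters here). If the schemes truly differ by 3 but the completers' difference has shrunk by s, the false-equivalence rate is about Φ(s / 0.924 − 2.128). With s = 0 this is 1.7%.

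**3. Simulation.** 130 per scheme, true reductions 10 and 7, a common Week 8 threshold for leaving, other withdrawal random up to 20% in total, two one-sided tests on completers.

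| Visit correlation | Leaving for poor response | Completers' difference | Hand formula | Simulated rate |
|---|---|---|---|---|
| any | 0% | 3.00 | 1.7% | 1.6–1.7% |
| 0.6 | 5% | 2.73 | 3.3% | 3.3% |
| 0.6 | 10% | 2.60 | 4.5% | 4.9% |
| 0.6 | 20% | 2.40 | 7.0% | 7.5% |
| 0.8 | 5% | 2.63 | 4.2% | 4.5% |
| 0.8 | 10% | 2.45 | 6.3% | 6.9% |
| 0.8 | 20% | 2.21 | 10.1% | 12.8% |

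The simulated rate is somewhat higher under strong selection because truncation also lowers the completers' SD. No extreme imbalance is needed: at the 10% setting, about 7% leave one scheme and 13% the other.

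**4. Other assumptions.**
- *Random withdrawal:* about 1 times nominal.
- *Selection at Week 4:* completers' difference 2.6 to 2.9, rate about 2% to 5%.
- *Leaving tied directly to final response:* in a second model with 129 per scheme, a correlation of 0.3 with 5% leaving gives 1.6 times nominal. A correlation of 1.0 with 20% leaving gives 21 times (difference 1.77).
- *Better responders leave the weaker scheme:* difference 3.6, rate 0.16 times nominal, so the bias reverses.
- *Margin:* M = 22 gives 3.3 and M = 25 gives 3.75. Scaling the smallest and largest shifts in the table (0.27/3 = 9.0%, 0.79/3 = 26.3%) by the margin, the hand formula gives 3.3% to 10.1% at M = 20, 3.5% to 11.7% at M = 22, and 3.9% to 14.5% at M = 25.

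**5. The Full Analysis Set as written.** If 20% of Week 12 values are replaced by one common mean, the difference becomes 0.8 × 3 = 2.4, even with random withdrawal. The variance falls to about 0.8 × 44 = 35.2, so with 129 per scheme SE = √(2 × 35.2 / 129) = 0.739. The rate is about Φ(0.6 / 0.739 − 2.128) = 9.4%; simulation gives 9.9%, or 5.9 times nominal. With withdrawal for poor response it was 7.7 to 43 times, worse than the Per Protocol set in each of these scenarios.

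**The case against.** The strongest reply is that no inflation factor belongs to the plan. The documents give no share leaving for lack of efficacy (item 5 pools it with other reasons), no withdrawal by scheme and no visit correlation. A reader might infer from the table that the plan inflates false equivalence by some fixed multiple. It does not: the factor runs from below 1 to about 21 according to what is assumed. The 20% rows also make every withdrawal a poor-response withdrawal, whereas the plan expects subjects to leave for various reasons. Without those rows the Week 8 range is 3.3% to 6.9%. This objection stands, and the figures should be read as scenarios.

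A reader might also infer that the Per Protocol set decides equivalence because the trial was sized on it. Items 1.10 and 1.11 only allow for withdrawal; they name no deciding set. The Full Analysis Set retains early leavers who have post-dose data. That stands too, but step 5 shows that this set, filled as planned, gives no protection.

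A third reply concerns the remedy. A mixed model recovers the truth when withdrawal depends on observed scores, which is the condition it assumes. The schedule shows no early-termination assessment, so subjects may leave on a worsening that is never recorded. This limits the fix but does not defeat it. With withdrawal partly on unobserved scores, the model gave 2.2 to 2.9 of a true 3.0, against 1.9 to 2.5 for completers. With withdrawal wholly on the unobserved state after Week 8, it gave 2.0 to 2.7.

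Finally, the same selection shrinks the drug-placebo difference. That is conservative and does not create false superiority.

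**Conclusion.** The concern holds in conditional form. By definition the Per Protocol set excludes those who leave for lack of efficacy or an adverse event, and discards their earlier scores. If withdrawal follows poor response at a similar level in both schemes, the bias favours equivalence.

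Under the Week 8 scenarios, with margin 3, the rate goes from 1.7% to about 3% to 13%. It is milder with Week 4 selection, larger when withdrawal depends on unobserved scores, nominal when withdrawal is random, and lower than nominal when better responders leave the weaker scheme. The documents do not show which of these applies. What they do show is that neither efficacy set, as written, guards the equivalence claim against the adverse case, and that no set is named to decide it. A low-cost change of wording is justified; confidence in the size of the effect is only moderate.

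**What to change.** For the equivalence analysis:
- Include subjects who took the assigned scheme without major protocol deviations up to their last on-drug HAM-A and have at least one post-baseline score. Judge adherence from the drug accountability already scheduled at Visits 2 to 4. State that subjects who left for lack of efficacy or an adverse event stay in.
- Analyse the observed Week 4, 8 and 12 scores with a repeated-measures mixed model, without mean fill, and take the Week 12 contrast. SAS MIXED is already listed under Statistical criteria.
- Use the same no-fill model in the Full Analysis Set, and require both sets to support equivalence.
- Keep the completers-only analysis as supportive.
- Add a sensitivity analysis in which withdrawal depends on unobserved scores.

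This changes analysis wording only and needs no new data or patients. The costs are a slightly wider Week 12 interval, some subjects with shorter exposure, and reliance on observed scores to explain withdrawal. Subjects who leave before Week 4 still contribute nothing to the revised set. Where withdrawal depends on unobserved scores, the model reduces the bias but does not remove it, which is why the sensitivity analysis is needed.
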